# Novapak Prospective Observational Clinical Trial Form Statistical Analysis Plan

Version 1.0

Page 7 of 7

- The graded percentage of vertical height of the middle turbinate taken up by the adhesion using an ordinal scale (0-3) from procedure through 1-month post treatment.
- The measure control of bleeding by comparing Boezaart Surgical Field Grading Scale scores post operatively, prior to Novapak insertion and post Novapak insertion.
- The measure of healing by comparing Lund-Kennedy scores before surgery and at 2 weeks and 1-month post treatment.
- The measure of health by comparing subject scores from the SNOT-22 questionnaire before surgery and at 2 weeks and 1-month post treatment.

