4.1.2 Secondary Objective(s)

The secondary objectives of this study will gather data to support the effectiveness of Novapak's inherent features and claims of performance:

Adhesions – Sinus packing devices act as a space occupying stent to prevent raw tissues from contact and forming unwanted, obstructive tissue connections known as synechia or adhesions. This study will collect the number of adhesions observed by endoscopic examination as well as a grade of the adhesions based on the percentage of vertical height of the middle turbinate taken up by the adhesion. This data will be compared to historical data related to adhesions post sinus surgery.

Control of bleeding – Sinus packing devices control bleeding by absorption and pressure on the bleeding surfaces known as the tamponade effect. Chitosan a component of Novapak also has hemostatic properties. This study will collect data related to post-operative bleeding. Since bleeding can be different for each subject and based on the extent of tissue trauma; a baseline observation immediately post-surgery using the Boezaart Surgical Field Grading Scale will be collected. After the packing is applied the surgical field will be graded again. In addition, any residual bleeding will be observed and noted at the subject visits.

Aid in healing – Novapak acts as an adjunct to aid in the natural healing process by providing a moist environment for the tissues during the proliferation phase of wound healing. In addition, the chitosan component within Novapak has hemostatic properties and is antibacterial to reduce unwanted microbial action which could lead to inflammation. The physician will grade the sinuses before surgery and then at each subject visit using the Lund-Kennedy scoring system. In addition, the subjects will provide sinus health responses to the SNOT-22 questionnaire prior to surgery and again at each subject visit.

Novapak is a dissolvable sinus packing device that under normal use with daily irrigation will be eliminated from the sinuses without the need for removal from the physician. An observation of residual Novapak will be done by the physician at each subject visit. These observations will be compared to the subject's compliance to daily irrigation.

5. Study Design

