9.1 Schedule of Events

Table 4: Planned Visits, Procedural Events and Data Collection

Visit	Procedure	Data Collection
Pre-Surgery	Inform subject about the study requirements Ask shellfish allergy questions Schedule Surgery	Consent document signed SNOT-22 (subject)
Day 0	Endoscopic exam	Lund-MacKay Scores Lund-Kennedy Scores (baseline)
	Functional Endoscopic Sinus Surgery Other interventions if bleeding more than minimal	Procedural Details Boezaart Surgical Field Grading Scale (pre-packing) Boezaart Surgical Field Grading Scale (post-packing) Question: Bleeding controlled post packing? Collect Adverse Events and/or Device Deficiencies
Day 1, 2, 3...	Daily Irrigations	Subject records volume / date Subject records any Adverse Events
Day 14 (-2, +5)	Office Visit Endoscopic exam Observe for residual product (remove) Debride Adhesions (if necessary) Review Subject Irrigations Records	SNOT-22 (subject) Lund-Kennedy Scores Question: residual product? Score Adhesions (Valentine method) Question: Bleeding controlled? Collect Adverse Events and/or Device Deficiencies
Day 30 (-2, +12)	Office Visit Endoscopic exam Debride Adhesions (if necessary)	SNOT-22 (subject) Lund-Kennedy Scores

Medtronic Business Restricted

	Review Subject Irrigations Records	Score Adhesions (Valentine method) Collect Adverse Events and/or Device Deficiencies
--	------------------------------------	---

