9.13 Assessment of Efficacy

The following parameters will be used to assess the effectiveness of the Novapak device used according to device indications:

Adhesions – in order to show that Novapak acts a nasal stent to separate tissue or structures compromised by surgical trauma and separate and prevent adhesions between mucosal surfaces in the nasal cavity the study physician will count the number of adhesions present and grade the sinuses using the ordinal scale method published by Valentine 2010.

Control of bleeding – in order to show that Novapak controls minimal bleeding the study physician will grade the bleeding post-surgery and prior to packing using the Boezaart Surgical Field Grading Scale. After inserting the Novapak product with irrigation to hydrate the product the bleeding will be graded again using the same scale.

During the day 14 visit the physician will be asked if any bleeding is observed during the exam and prior to any debridement procedure.

Progression of healing – The Lund Kennedy endoscopic grading system will be used to show that Novapak acts as an adjunct to aid in the natural healing process. The physician will perform an endoscopic exam prior to surgery (to establish a baseline), at day 14 and day 30 visits (to show progressive healing).

Residual Novapak – Novapak dissolves naturally with daily irrigation. Any residual Novapak in the nasal cavity will be recorded at the 14 day visit and compared to the subject compliance to the daily irrigation log.

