10.1 Potential Risks

Medtronic follows rigorous Quality Assurance and Control procedures throughout the life of a product, from the business analysis phase through development, market release, and post-market surveillance. The risk analysis process for the Novapak Study, is being performed in accordance with ISO 14971 and will ensure that the level of risk is acceptable prior to starting the study.

There are no incremental risks introduced to the subject as a result of participation in this study.

There are inherent risks for nasal sinus surgery as well as any surgery where removal, cutting and modification of tissues are required. These risks include:

- Mild Bleeding
- Adhesions, tissue synechia
- Fatigue
- Infection
- Moderate Pain
- Inflammation and swelling
- Nasal Congestion
- Mild to moderate headaches
- Facial pressure

Nasal sinus packing in general has tried to address these surgical complications but may result in risks that are specific to the use of packing, as follows:

- Bleeding – present if packing is inadequate or bleeding is excessive– may require post-operative controls (e.g., suturing, cautery, more packing)
- Adhesions – present if packing is inadequate to separate tissue compromised due to surgical trauma – requires post-operative debridement of tissues which may lead to bleeding.
- Scarring - This risk is where the tissue heals abnormally

- Infection – due to introduction of bacterial during the surgery and/or if sterility is breached - packing could encourage bacterial growth if design controls are not in place to control bacterial growth.
- Toxic Shock Syndrome –defined as “A severe illness caused by infection with staphylococcus aureus and characterized by high fever of sudden onset, vomiting, diarrhea, and myalgia, followed by hypotension and in severe cases, shock; a sunburn like rash with peeling of the skin, especially of the palms and soles, occurs during the acute phase.”
- Respiratory Obstruction – physical obstruction of the breathing pathway – This harm may occur from stent migration and cause difficulty breathing (i.e., hypoxia, dyspnea)
- Aspiration of the packing – causes respiratory obstruction with tachypnea can lead to aspiration pneumonia, urgent medical intervention may be necessary
- Pneumonia - If the stent were aspirated, pneumonia may occur. The patient may be treated with IV medication.

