- Potential toxicity reactions – components of the packing could lead to a toxicity reaction due to a non-biocompatibility reaction occurring, but the reaction would not be expected to go beyond an inflammatory response. (i.e., redness, swelling, etc.)
- Potential allergic hypersensitivity reactions – components of the packing could lead to an allergic hypersensitivity reaction - A patient may experience edema and difficulty breathing with IV medications used as medical intervention.
- Foreign Body Reaction - Potential tissue interactions with packing components, fragments, or surface texture. In addition to an inflammatory response, it usually includes the formation of a foreign body granuloma, or encapsulation around a foreign object. Medical intervention may be taken to remove the product.
- Inflammation - This harm includes local irritation from the product. This risk may require Oral medication to reduce inflammatory response.
- Fever - A medium-low grade fever may develop. This risk may require Oral medication to reduce inflammatory response.
- Device Fragments in Patient – If a device fragments migration of pieces of the stent could result in possible medical intervention needed
- Pain – during post-operative removal of non-dissolving packing devices most patients have reported some mild temporary pain.
- Decreased Therapeutic Response – The packing may not perform as expected and not control the risks as intended. It would not result in surgical correction but may require a minor medical intervention.

The use of the Novapak Nasal Sinus Packing and Stent may involve the risks listed above for all packing type devices, with the exception of pain upon removal, since it dissolves away with irrigation. There may be other discomforts and risks related to the Novapak Nasal Sinus Packing and Stent device and/or this study that are not foreseen at this time.

Medtronic Business Restricted

These are the current risks of Novapak seen in the field based on reports to our complaint system: (number of reported events as of June 24, 2022)

- Irritation – potential shellfish hypersensitivity (1)
- Post-operative bleeding requiring secondary controls (3)
- Post-operative device migration to oral cavity (1)
- Post-operative edema and pain (2)

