### 4.2 Secondary Objectives

The secondary objectives of this study will gather data to support the effectiveness of Novapak's inherent features and claims of performance:

Adhesions – Sinus packing devices act as a space occupying stent to prevent raw tissues from contact and forming unwanted, obstructive tissue connections known as synechia or adhesions. This study will collect the number of adhesions observed by endoscopic examination as well as a grade of the adhesions based on the percentage of vertical height of the middle turbinate taken up by the adhesion. This data will be compared to historical data related to adhesions post sinus surgery.

**Control of bleeding** – Sinus packing devices control bleeding by absorption and pressure on the bleeding surfaces known as the tamponade effect. Chitosan a component of Novapak also has hemostatic properties. This study will collect data related to post-operative bleeding. Since bleeding can be different for each subject and based on the extent of tissue trauma; a baseline observation immediately post-surgery using the Boezaart Surgical Field Grading Scale will be collected. After the packing is applied the surgical field will be graded again. In addition, any residual bleeding will be observed and noted at the subject visits.

Aid in healing – Novapak acts as an adjunct to aid in the natural healing process by providing a moist environment for the tissues during the proliferation phase of wound healing. In addition, the chitosan component within Novapak has hemostatic properties and is antibacterial to reduce unwanted microbial action which could lead to inflammation. The physician will grade the sinuses before surgery and then at each subject visit using the Lund-Kennedy scoring system. In addition, the subjects will provide sinus health responses to the SNOT-22 questionnaire prior to surgery and again at each subject visit.

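### SAP 7.9.2 confines control of bleeding to the Day 0 Boezaart change, so later bleeding that needs a secondary control is left out of the effectiveness result

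*SAP*

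**What the plan says.** SAP 7.9.2 lists one item for bleeding: "The measure control of bleeding by comparing Boezaart Surgical Field Grading Scale scores", with the timing "post operatively, prior to Novapak insertion and post Novapak insertion". CIP 9.8 places both grades at the surgical visit.

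The stated objective is wider. CIP 4.1.2 says "This study will collect data related to post-operative bleeding", and SAP 4.2 adds that "any residual bleeding will be observed and noted at the subject visits". Two further items are collected but do not appear in SAP 7.9.2:

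- On Day 0, CIP Table 4 has "Question: Bleeding controlled post packing".
- At Day 14, CIP 9.13 says "During the day 14 visit the physician will be asked if any bleeding is observed during the exam and prior to any debridement procedure". The Synopsis and Table 4 word this item differently, asking whether bleeding is controlled.

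CIP 10.1 names bleeding as a risk specific to packing, one that "may require post-operative controls (e.g., suturing, cautery, more packing". Its field complaint list includes "Post-operative bleeding requiring secondary controls (3", where the bracketed figure is the number of reports.

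On capture, CIP 9.10 sends adverse events found at unscheduled visits to the AE form, and CIP 11.1 requires treatment of an AE to be reported. CIP Table 8 exempts mild bleeding from reporting for 5 days after surgery unless it worsens or lasts longer. SAP 7.9.1 counts AEs that are device-attributed or of undetermined cause, and all AEs.

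**The concern.** The device typically stays in place for 7 to 14 days (CIP 6.1), and the indication concerns bleeding after surgery. The only planned effectiveness measure of bleeding ends minutes after insertion. Bleeding on, say, day 3 that is treated and stopped is a plain sign that control did not last, yet it cannot move that measure. The omission works in one direction: counting such events could only leave the bleeding summary unchanged or make it less favourable.

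The stake is the labelling claim. CIP 5.2 says the data will support claims that include control of minimal bleeding, and CIP 3.2 says the study supports a CE Mark submission. A reader of the effectiveness section would see immediate haemostasis and could take it for post-operative control.

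**Working it through.** The documents give no bleeding-control rate, threshold or power figure, and SAP 6 says that 75 was not set by statistical methods. There is no planned figure to reproduce. The check traces a case through the plan and then illustrates its size.

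**Trace.** Take a subject whose grade improves on Day 0, who bleeds on day 3, is treated, and is not bleeding at Day 14.

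| Item | Effect of the event |
|---|---|
| Boezaart change (SAP 7.9.2) | None; both grades precede it |
| Day 0 bleeding question (CIP Table 4) | None; answered before it, and not in SAP 7.9.2 |
| Day 14 item as worded in CIP 9.13 | None; asks about bleeding seen at the exam, and not in SAP 7.9.2 |
| Day 14 item as worded in CIP Table 4 | Unclear; a physician aware of the treatment could answer no. Not in SAP 7.9.2 |
| All-AE count (SAP 7.9.1) | Adds one event if reported |
| Device-attributed or undetermined AE count (SAP 7.9.1) | Adds one event if so classified |

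The event can reach the safety counts but no analysed effectiveness measure.

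**Complaints (CIP 10.1).** Total 1 + 3 + 1 + 2 = 7; bleeding needing secondary controls is 3/7 = 43%, the largest single category. The exact 95% interval is 10% to 82%, which shows how little seven reports can establish.

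**How likely is at least one event?** Assume 75 treated subjects and a rate p of bleeding that needs a secondary control. Expected number = 75p; P(at least one) = 1 − (1 − p)^75.

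| Assumed p | Expected | P(at least one) |
|---|---|---|
| 1% | 0.75 | 53% |
| 2% | 1.5 | 78% |
| 5% | 3.75 | 98% |
| 10% | 7.5 | 99.96% |

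**What the missing line would show.** For k subjects of 75, the exact (Clopper-Pearson) limits are the 0.025 quantile of Beta(k, 76 − k) and the 0.975 quantile of Beta(k + 1, 75 − k). For k = 0 the lower limit is 0.

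| k (assumed) | k/75 | Exact 95% CI |
|---|---|---|
| 0 | 0% | 0 to 4.8% |
| 1 | 1.3% | 0.03 to 7.2% |
| 2 | 2.7% | 0.3 to 9.3% |
| 4 | 5.3% | 1.5 to 13.1% |
| 8 | 10.7% | 4.7 to 19.9% |

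Under the current plan the bleeding-effectiveness result is the same in all five rows.

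**The case against.** The strongest reply is that the event is not lost. Bleeding that needs treatment is an adverse event, safety is the primary objective, and SAP 7.9.1 counts it. CIP 11.5.1 assigns a MedDRA term to each AE, so a safety table might well show bleeding. This stands, and it limits the point. But the SAP specifies no breakdown by term or by treatment given, and nothing links the event to the bleeding claim. An event judged related only to the procedure adds one to the all-AE count and nothing else.

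Second, a reader might infer that the plan scores these subjects as successes, or would report 75 of 75 as controlled. The documents do not support that. They define no success or responder category, CIP 13.1 calls the analyses descriptive, and the Boezaart comparison remains a true statement about immediate haemostasis.

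Third, a reader might infer that the Day 14 question could never reveal such a case. That follows from the CIP 9.13 wording but not from the Table 4 wording.

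Fourth, calling this the device's main haemostatic failure goes too far: it rests on seven complaints with no denominator.

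Fifth, not every such bleed is a device failure. CIP 10.1 attributes bleeding to inadequate packing or to excessive bleeding, the claim concerns minimal bleeding, and CS3600 is expected to dissolve in about a week (CIP 6.7), so a later bleed may follow its disappearance. This is a sound reason not to label every such subject as uncontrolled. It is not a reason to leave the events out of the bleeding summary.

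**Conclusion.** The point holds as an omission. SAP 7.9.2 measures control of bleeding on Day 0 only, and neither document says how later bleeding that needs a secondary control enters the effectiveness result. That result can therefore look more favourable than the post-operative experience, while the event sits unseparated in the AE counts.

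The size cannot be known from the documents. With 75 treated subjects, one or more such events is more likely than not at an assumed rate of 1% (53%) and close to certain at 5% (98%). The rates and the values of k are assumptions. The denominator is one too, since CIP 8.1 expects that some enrolled subjects may not receive packing. The primary safety analysis does not depend on this point; the support for the bleeding claim does.

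**What to change.** Add one descriptive measure to SAP 7.9.2 and CIP 9.13: the number and percentage, with exact 95% CI, of subjects with bleeding after the post-packing grade that required a secondary control (for example suturing, cautery or more packing), through Day 14 and through Day 30, taken from the AE and unscheduled-visit forms. Report it beside the Boezaart change and the answers to the Day 0 and Day 14 bleeding questions. Use one wording for the Day 14 question throughout the CIP. No rule that reclassifies these subjects as not controlled is needed; cause and relatedness can be listed with each event.

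State also that any bleeding needing a secondary control is recorded on the AE form, even within the 5-day mild-bleeding exemption in CIP Table 8. Otherwise the count depends on how a site reads that exemption.

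This is a reporting rule and changes nothing in patient care. The cost is wording in two documents, one derived variable from data largely required already, and possibly a less favourable bleeding summary. No extra subjects are needed.

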## 7.10 Changes to Planned Analysis

Not applicable.

## 8. Validation Requirements

Statistical programming code that affects the result of the main analysis for the primary objective shall be validated using Level I validation.

Programming code that affects the result of the main analysis for the secondary objectives shall be validated using at least Level II validation.

In addition, those main statistical analyses that are planned for publication and have not been previously validated should be validated with at least Level II validation.

Level III validation may be used for any previously validated program where only minor/administrative changes were made (e.g., change the location of the data directory). Additional measures may need to be validated as determined by statistical management.

